### 3.7.2 Sample Size Calculation for Mother-Infant Dyads

The sample size for mother-infant dyads was calculated using the two-sample independent t-test. This was based on a previous study and this study's primary outcome (Rao, Udani, & Nanavati, 2006). The two-tailed comparison group was used in the sample size calculation using the formula below. The mean difference in weight gain was 8.41 (Rao et. al., 2006) pre and post-intervention, while 0.8 was the standard deviation. These values were applied in the formula based on the study done by Rao et., al (2006).

$$\text{The formula, } n = \frac{2[Z\alpha/2 + Z\beta]^2 S^2}{(\mu_1 - \mu_2)^2}$$

$$\text{Thus, } Z\alpha/2 = 1.96 \quad Z\beta = 0.842$$

$$\mu_1 - \mu_2 = 0.54 \quad S = 0.8$$

$$\text{The formula, } n = \frac{2[1.96 + 0.84]^2 [0.8]^2}{(0.54)^2}$$

$$n = \frac{2 [ 2.802 ]^2 (0.64)}{0.29}$$

$$n = \frac{2 [ 7.85 ] (0.64)}{0.29}$$

$$n = \frac{10.05}{0.29}$$

Thus,  $n = 34.65 = 35$  subjects for each group.

Additional 30% = 50 subjects for each group.

An additional 30% was added to the estimated sample size to account for possible missing values and non- responses. The final sample size calculated was 50 for the sample population, and 50 for the experimental group.

The two groups of preterm infant-mothers were recruited from those who were admitted to the NICU. The first set of samples ( n=50) was recruited from early February 2018 until July 2018. The preterm infant-mother dyads who were admitted within these months were allocated to the control group, while recruitment for the experimental group of preterm infant-mother dyads (n=48) was initiated from early September 2018 until April 2019, after completion of the intervention program for the nurses. In both groups, the sample size for the control group was (n=48) and the experimental group (n=48), for a total sample size of (n=96).

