### **3.16 Data Collection Method**

There were three phases to this study: Phase I, Phase II, and Phase III. Phases included:

i)In phase, I, the data ( $T_0$ ,  $T_1$ , and  $T_2$ ) for the control group of mother-infant dyads was collected within six months until the data met the requirements of the study. Data collection for the control group's mother-infant dyads started in early February 2018, and continued until the end of July 2018. Assessment of function in routine clinical practices in the control group of mother-infant dyads and outcomes of premature infants was recorded in the KCPR booklet provided for the control group of mothers within the stipulated time and then analysed.

ii)In phase II, one group pretest-posttest for nurses' data collection process was conducted 2 months after the control group of mothers' data collection was completed. The data collection for nurses and the intervention commenced in early August 2018 and continued to the end of September 2018. Quantitative data (Questionnaire II) were collected at pretest, and one week after the structured KC-EP was conducted for nurses the posttest data were analyzed. The structured KC-EP for nurses included knowledge, skills, and attitude prior to KC guidelines and protocol. The specific aims were to educate nurses in the content areas noted above. The reasons for implementing a neonatal KC protocol for mother-infant dyads were generally considered in terms of the method of holding the premature infant directly, breastfeeding rates and looking at the effects of KC outcomes.

iii) In phase III, the data ( $T_0$ ,  $T_1$ , and  $T_2$ ) for the experimental group of mother and premature infant were collected within seven months. In the experimental group, data collection for mother-infant dyads began in early October 2018 and was completed by the end of April 2019. The KC-EP for mothers was conducted by the nurses in the NICU for them to implement KC with their premature infants. The structured KC-EP was comprised of theory and practical sessions to fulfill the objectives of this study. The post-intervention assessment

of quantitative data (Questionnaire I) on mother-infant dyad compliance and outcomes of KC implementation (KCPR) commenced from the premature infant's recruitment day. The data was plotted to begin from the inclusion criteria age until 3-months-old corrected age.

[figure not shown]

Figure 3.2: Flow Chart Showing the Three Phases of Data Collection

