### **3.16.2 Data Collection Method for Mothers in the Experimental Group**

The recruitment of the experimental group of mothers was based on premature infant's day of admission to the NICU after data collection from the nurses was completed. This was done to keep mothers in the experimental group from being exposed to the control group during their hospital stay. Both mothers and premature infants were medically and surgically stable, and mothers were willing to perform KC. For the experimental group of mothers, data collection was carried out over seven months from early October 2018 to the end of April 2019, after the nursing intervention program for nurses (KC-EP) had been completed. An average of two to four mothers was recruited per week.

The mother-infant dyads were recruited within 48 hours, as soon as they were clinically stable and eligible to perform KC. Samples were selected by the researcher, who returned after 48 hours to meet mothers interested in the study and agreed to complete the consent form. Prior to recruitment, consent was sought on a voluntary basis from all (n=48) mothers (Appendix B). The researchers explained to the mothers how to answer the questions (Questionnaire I) provided in English and Bahasa Malaysia. At T0, the questionnaire was given to all participants before the KC-EP was conducted. Each mother had her own identification code number put on the outside of the envelope to match Questionnaire I at T0, T1, and T2 accordingly. The identification numbers started from MEG01(mother experimental group 01).

In addition, signs of readiness to suckle, characterized by moving the tongue and mouth, and the desire for sucking, such as sucking fingers or mother's skin, were observed. As mentioned by Nyqvist (2012), early sucking competence is only observed from 29 weeks postpartum age onward, with the attainment of full breastfeeding as early as 32 weeks postpartum age. Those premature infants born before 32 weeks were given intravenous or nasogastric feeding.

The experimental group, comprised of mother-infant dyads, received a detailed verbal explanation on KC-EP. The contents of the module were verified by health care

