### **3.17 Method of Data Collection for Nurses**

The nurses were screened and recruited based on universal sampling. Method of data collection for nurses was similar to that for mothers, whereby, prior to the KC-EP for nurses, pretest data on nurses' perception, knowledge, and practice were collected using the KCQ tool in Questionnaire II. The data for nurses were collected within a 2 month period from 1st August 2018 to 30th September 2018 for the pretest-posttest groups of nurses. The researchers briefed the nurses and encouraged them to take part in the study by presenting verbally brief information to the head nurse in charge of the unit, with two forms of consent given to the nurses on the same day as the pretest program. All nurses who attended were recorded with their name, identification code number, date of attendance and signature in order to plan the date for their following posttest. To ensure confidentiality and privacy, each returning questionnaire was assigned an identification code number. The consent form together with the questionnaire was stamped, starting with nurse 01(N01), with the code number in the top right corner. If the nurses refused to continue with the study, they were instructed to notify the researcher and ask for a withdrawal. Upon receiving an application for withdrawal from the study, the researcher found and destroyed the questionnaire, which was submitted based on the code number. The pretest (Questionnaire II) was given to all nurses before the KC-EP was administered to them. The nurses were instructed to complete Questionnaire II, which took approximately 15 to 20 minutes to complete, without reference to any resources before the KC-EP session for nurses was conducted. Nurses were asked to return the questionnaires upon completion, with one copy of the informed consent. All nurses were advised to keep one copy of the informed consent for their records. Following the completion of the KC-EP, the nurses were told of the posttest sit after the 7th day of the pre-test and intervention program. The same structured Questionnaire II was administered to the nurses at the posttest. Data collection among nurses was conducted within the stipulated time.

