Next, the researcher collected the group of participants from among the nurses, made them comfortable, and orientated them to the study. She then administered the structured quantitative-based Questionnaire II for nurses. All nurses were instructed not to interact with each other, and their doubts were clarified. The questionnaire took 10 to 15 minutes to complete; after completion the researcher asked the nurses to return the pre-test questionnaires as well as a copy of the informed consent form. All nurses were instructed to keep one copy of the informed consent form for their records. On the same day, nurses were asked to return the completed questionnaire to the researcher. Each questionnaire returned was given an identification code number to ensure confidentiality and privacy. For each set of questionnaires (pretest and post-test), the consent form and the questionnaire were labeled with a code number, beginning with N01 for the nurses, at the right top corner. The nurses' baseline data were gathered on demographic characteristics and KCQ tools (perception, knowledge and practice) regarding the KC technique. After the pre-test phase, the structured kangaroo care educational program (KC-EP) for nurses was conducted within two weeks for all  $n=47$  nurses. The program was delivered in English for the theory, and the practical

session included the showing of videos related to the KC transferring technique by the researcher. All nurses were informed to sit for the required post-test on the 7th day after the pretest phase and the KC-EP teaching module. The same structured Questionnaire I was administered at the post-test, and nurses were required to demonstrate the KC standing and sitting procedure. A checklist was provided for each nurse to assess her confidence and skills in relation to the KC technique. The collection of nurses' data lasted from 1st of August 2018 until the 30th of September 2018.

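### The plan's dates leave no gap between the control phase and nurse training, although it states 2 months, so late-enrolled controls may have been inpatients during training

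*Combined protocol and SAP*

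**What the plan says.** The design is sequential in one unit: control dyads first, then the nurse programme, then experimental dyads.

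- **Gap.** Section 3.16 says the nurse phase "was conducted 2 months after the control group of mothers" had completed data collection.
- **Control phase.** Section 3.16 says collection of control data (T0, T1 and T2) "started in early February 2018, and continued until the end of July 2018". Section 3.18 also says it was completed by then. Sections 3.7.2 and 3.16.1, however, describe *recruitment* of controls as running to July, in 3.16.1 to the end of the month.
- **Nurse phase.** Section 3.16 says nurse data collection and the intervention "commenced in early August 2018 and continued to the end of September 2018". Section 3.17 says "The data for nurses were collected within a 2 month period from" 1 August to 30 September 2018, and 3.18 agrees.
- **Length of training.** Section 3.18 says the nurse programme "was conducted within two weeks for all" 47 nurses. Appendix J schedules theory and practical sessions across August and September 2018.
- **Experimental phase.** Section 3.7.2 says recruitment "was initiated from early September 2018 until April 2019", and places this after the nurse programme was complete. Sections 3.16 and 3.16.2 say early October.
- **Purpose of the phasing.** Section 3.16.2, on recruiting the experimental group only after the nurse phase: "This was done to keep mothers in the experimental group from being exposed to the control group during their hospital stay". Section 3.3.2 gives contact between mothers on one ward as a reason not to randomise.

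**The concern.** Separation in time is the main protection this non-randomised design has against contamination between arms, and the plan states a separation that its dates do not deliver.

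The route to contamination is specific. All NICU nurses are invited to training, whose stated purpose (3.15.3) includes promoting KC and breastfeeding to mothers in the NICU. Section 3.17.1 expects nurses to use the 7 days before the post-test for hands-on practice in the unit. On the October date, any study dyads still in the unit in August and September are controls. Section 3.16.1 lets control mothers do KC if they are interested, so encouragement by newly trained nurses could change what controls receive. Weight gain and length of stay (LOS) are the primary outcomes (3.9, Section B), and LOS accrues entirely in hospital. Contamination of this kind would shrink the difference between arms.

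**Working it through.** Early in a month is taken as day 1 to 7 and the end of a month as its last day.

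**1. The stated gap.** Stated: 2 months. From the dates: control phase ends 31 July 2018, nurse phase starts 1 August 2018, so there are 0 days between. The stated figure does not reproduce. The nurse phase itself lasts 31 + 30 = 61 days, about 2 months.

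**2. Can control recruitment and control follow-up both end in July?** Enrolment is at 28 to 36+6 weeks corrected age (3.7.1). T2 is at week 52, read as infant age as in Table 3.2.

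- Enrolment to T2: 52 − 28 = 24 weeks; 52 − 36.86 = 15.1 weeks.
- Enrolled on 31 July 2018: T2 falls between 14 November 2018 and 15 January 2019.
- For T2 by 31 July 2018: the last enrolment must be by 13 February (at 28 weeks) to 16 April (at 36+6 weeks).
- Section 3.16.1 gives 2 to 4 mothers per week. For the 50 controls in 3.7.2, 50/4 = 12.5 weeks and 50/2 = 25 weeks, so from 1 February the last enrolment falls between about 29 April and 26 July. Even 29 April is past the latest cut-off.

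Section 3.18 instead times the post-tests at 1 and 3 months after discharge. On that reading T2 comes more than 3 months after enrolment, so enrolment would have to end before 30 April. The statements still conflict.

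**3. Controls in the unit on 1 August.** With uniform recruitment from 1 February to 31 July (181 days) and a remaining stay of L days after enrolment, the share still inpatient on 1 August is about L/181.

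| Assumed L | Share | Of 48 controls |
|---|---|---|
| 11 days | 11/181 = 6.1% | 3 |
| 36 days | 36/181 = 19.9% | 10 |

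The 11 and 36 days are the stays quoted in section 1.2 for births at 32 to 36 weeks. They come from an outside foundation, not from this unit, and are used here only as an assumed range. At 4 per week the last control enrols about 29 April, 94 days before 1 August, and the share could be near zero.

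As a ceiling, if each of these controls took on the whole experimental effect, the difference in means would shrink by the same fraction, 6% to 20%.

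**4. Experimental arm.** A start on 1 September overlaps the nurse phase by 30 days and a start on 7 September by 24 days. A start on 1 October gives 0 days. If training took two weeks from early August (3.18), it ended before September and even the 3.7.2 date gives no overlap with training itself.

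**The case against.** A reader might infer that both arms overlap the change in nursing practice. The documents do not support that as a flat statement. A gap of zero means that the phases abut.

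- **Control arm.** Sections 3.16 and 3.18 say control data were complete by the end of July. If that were true, no control would have been in the unit in August. The follow-up arithmetic makes it incompatible with recruitment to the end of July, but it does not show which statement is wrong. Overlap is therefore possible, not established.
- **Experimental arm.** Overlap rests on 3.7.2 alone, and that sentence itself places recruitment after the nurse programme. It also needs training to have run past August, on which 3.18 and Appendix J differ. Sections 3.14 and 3.18 say the researcher delivered the mothers' programme (3.16 says the nurses did), so a September recruit need not have missed the intervention.
- **The 2 months.** The phrase may be a slip for the length of the nurse phase, and no section states a washout purpose. That is a fair reading. It would remove the contradiction in wording and leave a plan with no separation at all.
- **The 6% to 20%.** The range is fragile in both directions. Eligibility starts at 28 weeks, so stays may be longer than those quoted. Enrolment follows admission and stabilisation, so the remaining stay is shorter than the full stay. Recruitment may not have been uniform.

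These points limit the size and certainty of the contamination. They do not remove the date conflicts.

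**Conclusion.** Three contradictions are established from the text alone: a stated gap of 2 months against a dated gap of 0 days; control recruitment to the end of July against T2 completion by the end of July; and experimental recruitment from early September against early October.

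Contamination of late-enrolled controls is plausible but its extent is unknown: about 6% to 20% of controls under uniform recruitment and remaining stays of 11 to 36 days, and possibly near zero under fast recruitment. Experimental overlap with training arises only if the September date is right and training ran past August. The documents do not show which start date is correct. This should be put right because it bears on the main safeguard of the design and costs little to address.

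**What to change.** 1. Reconcile the dates in 3.7.2, 3.16, 3.16.1, 3.16.2 and 3.18 against the recruitment log, give separate dates for end of enrolment and end of follow-up in each arm, and state when nurse training ended. Correct or remove the statement that the nurse phase came 2 months after control data collection.
2. If the dates can still move, stop control enrolment early enough that controls are discharged before nurse training starts.
3. If the dates are fixed, record each control's inpatient days after 1 August 2018. Add a sensitivity analysis that excludes controls enrolled after a pre-set calendar date before 1 August, and any experimental dyads enrolled before nurse training ended.
4. Define the exclusion by enrolment date, not by being an inpatient on 1 August. Inpatient status on a fixed day preferentially picks out long stays, and dropping those controls would bias the LOS comparison.

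The cost is a short delay if dates move, or otherwise a smaller sample in one sensitivity analysis. For example, a cut-off 36 days before 1 August would remove about 10 of 48 controls under uniform recruitment. Controls enrolled earlier with long stays would remain, and the recorded inpatient days would show how much exposure is left.

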### 3.16.1 Data Collection Method for Mothers in the Control Group

Based on the day of the preterm infant's admission to the NICU, the researcher screened and recruited its mother into the control group. The mothers and premature infants were medically and surgically stable. The researchers chose mothers who were ready and returned after 48 hours to meet those who were interested to participate in the study. The selection was determined according to the mother's and premature infant's condition (clinically stable and eligible to perform KC), while the length of gestation had to be between 28 to 36/6 weeks. The study samples were selected from early February 2018 to the end of July 2018, within six months of the mothers in the control group. An average of two to four mothers was recruited per week. Mothers had to fill out a consent form. Consent was obtained from all mothers before they were recruited. The researchers contacted the participants in order to give an explanation of what was involved.

Questionnaire I for mothers was provided in an English and bahasa Melayu version. All mothers were given the same questionnaire in three phases ; T0, T1, and T2. At T0, all mothers were given the questionnaire on a voluntary basis to determine their perspectives on the implementation of KC as a baseline. The researchers created an identification code number for each of the mothers to be placed on the envelopes. Thus, mothers' answers could be matched for the T0, T1, and T2 questionnaires. The identification code started from MCG01 (mother control group 01). After a welcome speech and briefing (10 to 15 minutes), the questionnaires were given to the mothers to fill in and then collected. The mothers in the control group were also given a Kangaroo Care Progress Record (KCPR) booklet to record weight gain, feeding status, the routine practice of KC in the clinical setting and after discharge until 3 months old but without any information or input related to KC.

The control group mothers came for visits and saw their preterm infants once a day for 30 minutes to 1 hour, and exercised KC if they were interested. This was the NICU's routine practice. The control group of mothers continued routine ward practice and standard hospital care. Mothers who declined to participate during the time of the study were excluded. For participation in the study, a small token gift was given to (n=48) mother-infant dyads at the control group.

Upon their premature infant's discharge from the hospital, the mothers were reminded to answer the same standardized questionnaire (QI) for T0, T1, and T2. The following posttest questionnaires (Questionnaire I: enclosed in the envelope) were given to the mothers at the NICU or the Pediatrics Clinic on the 1st and 3rd month, when they came for their premature infant's follow-up, and were returned the same day. Consequently, some of the data were collected and sent by email if the mothers could not keep to the time (received on the same day).

### **3.16.2 Data Collection Method for Mothers in the Experimental Group**

The recruitment of the experimental group of mothers was based on premature infant's day of admission to the NICU after data collection from the nurses was completed. This was done to keep mothers in the experimental group from being exposed to the control group during their hospital stay. Both mothers and premature infants were medically and surgically stable, and mothers were willing to perform KC. For the experimental group of mothers, data collection was carried out over seven months from early October 2018 to the end of April 2019, after the nursing intervention program for nurses (KC-EP) had been completed. An average of two to four mothers was recruited per week.

The mother-infant dyads were recruited within 48 hours, as soon as they were clinically stable and eligible to perform KC. Samples were selected by the researcher, who returned after 48 hours to meet mothers interested in the study and agreed to complete the consent form. Prior to recruitment, consent was sought on a voluntary basis from all (n=48) mothers (Appendix B). The researchers explained to the mothers how to answer the questions (Questionnaire I) provided in English and Bahasa Malaysia. At T0, the questionnaire was given to all participants before the KC-EP was conducted. Each mother had her own identification code number put on the outside of the envelope to match Questionnaire I at T0, T1, and T2 accordingly. The identification numbers started from MEG01(mother experimental group 01).

In addition, signs of readiness to suckle, characterized by moving the tongue and mouth, and the desire for sucking, such as sucking fingers or mother's skin, were observed. As mentioned by Nyqvist (2012), early sucking competence is only observed from 29 weeks postpartum age onward, with the attainment of full breastfeeding as early as 32 weeks postpartum age. Those premature infants born before 32 weeks were given intravenous or nasogastric feeding.

The experimental group, comprised of mother-infant dyads, received a detailed verbal explanation on KC-EP. The contents of the module were verified by health care

professionals, including two neonatalogists, a nursing professor, a nursing lecturer, and three head nurses who specialized in neonatal nursing. The contents of the KC module were: the meaning of the term KC, benefits of KC, precautions against any abnormality in parameters (temperature, respiratory rate (Sao2), heart rate perfusion (color), and tolerating feeding well in the 24 hours before performing KC. The program included the showing of videos on the KC procedure (standing and sitting transfers). The mothers were prepared with a KC information handout and a leaflet on KC associated with the KCPR. The booklet was developed based on research articles and health-care professional modules on KC in relation to physical, emotional and verbal support, on encouraging mothers to hold their premature infant in the right position for KC and on performing KC for the benefit of their premature infant. KC was started once the preterm infant had been deemed clinically stable. Baby pouches and diapers were provided to all mothers in the experimental group. The researcher developed a personal goal setting self-motivation routine to help mothers achieve the potential best practice of KC for their preterm infants. Self-motivation is a vital part of emotional intelligence and something that is needed by any mother involved in doing KC. It keeps mothers motivated to undertake KC with a minimum period of 1 hour a day during day and night, accumulating to 4 to 5 hours per week. For preterm infants undergoing intravenous fluid therapy, mothers were expected to sit in a comfortable chair near the incubator or cradle of the preterm infant (to facilitate sustained KC).

Data on weight gain (body weight in grams), KC duration in a week (hour/per week), and breastfeeding status (weeks) were collected from T0 to T2. Additionally, the experimental group of mothers maintained documentation of the outcomes of their preterm infant from the day of recruitment until the infant was 3 months old. The diaries provided information on the prospective longitudinal progress outcomes of the premature infants. Each KCPR booklet was labeled as an experimental group progress record and included the identification code

number of the mother-infant dyad. However, if the mother was unable to record the data, she instructed a close family member to help at home.

Lastly, the same quantitative data was collected from the mothers at T1 and T2 post structured KC-EP. In order to assess the mothers' perspectives on KC performance, perception, knowledge, perceived barriers, and stress were determined. The program was constructed for the introduction of KC into the NICU as a standard care procedure. Therefore, after the return home or at least for the first 3 months of the preterm infant's life, KC should be continued.

